## 1. INTRODUCTION

This document contains the statistical analysis plan (SAP) for the exposure-response analysis of household air pollution (HAP) exposure and infant severe pneumonia. HAP exposure was measured during 24-hour periods repeatedly during pregnancy and infancy. HAP indicator pollutants include air concentrations of fine particles, black carbon, and carbon monoxide. Severe pneumonia is one of the four primary outcomes of the HAPIN trial. This SAP covers the exposure-response analysis of severe pneumonia and other respiratory endpoints of the trial. The pneumonia outcomes analyzed were detected by active surveillance, record review, and verbal autopsy.

### 1.1. Background and Rationale

Globally, nearly 3 billion people rely on solid fuels for household cooking and heating, the vast majority in low- and middle-income countries (LMICs). The emissions from solid fuel use comprise a major source of household air pollution (HAP), which is recognized as an important environmental risk factor for morbidity and mortality, accounting for an estimated 2.3 million premature deaths globally. Previous large-scale interventions have provided cleaner cookstoves but have failed to reduce exposure to levels that might be required to produce meaningful or detectable health improvements. There have been no large-scale field trials with liquefied petroleum gas (LPG) cookstoves, likely the cleanest scalable intervention.

The HAPIN trial will provide evidence to inform national and global policies on scaling up LPG stoves among vulnerable populations. Ultimately, this will facilitate deeper policy-level discussions as well as identify requirements for initiating and sustaining HAP interventions globally.

A large burden of severe pneumonia is attributed to HAP in young children in low- and middle-income countries, who often have high prenatal and postnatal HAP exposure. Previous cleaner biomass stove and clean fuel intervention trials have failed to provide unequivocal evidence of intervention effects on pneumonia incidence in infants, despite observational evidence that exposure to biomass smoke and other sources of combustion-generated pollution cause childhood pneumonia. Failure to provide evidence of the expected effects in intervention trials might hinder promotion of cleaner cooking stoves for the health benefits. A Exposure-response analysis of the causal relationship between HAP and pneumonia may further our understanding of the expected magnitude of effects from interventions.

### 1.2. HAPIN Study Overview

The aim of the HAPIN study is to conduct a randomized controlled trial of LPG stove and fuel distribution in 3200 households in four LMICs (India, Guatemala, Peru, and Rwanda) to deliver rigorous evidence regarding potential health benefits across the lifespan. Each intervention site recruited 800 pregnant women (aged 18- $<35$  years, 9 to  $<20$  weeks' gestation), and randomly assigned half their households to receive LPG stoves and an 18-month supply of LPG. Controls did not receive the intervention at the commencement of the trial and were generally expected to continue cooking with solid biomass fuels; the control group was compensated for

their participation in the study. The mother was followed along with her child until the child was 1 year old. In households with a second, non-pregnant older adult woman (aged 40 to <80 years) we also enrolled and followed her during the 18-month follow-up period to assess cardiopulmonary, metabolic, and cancer outcomes. To optimize intervention use, we implemented behaviour change strategies. We assessed cookstove use, conducted repeated personal exposure assessments to HAP (PM2.5, black carbon, carbon monoxide), and collected dried blood spots (DBS) and urinary samples for biomarker analysis and biospecimen storage on all participants at multiple time points. The primary outcomes were birth weight, severe pneumonia, and stunting at age 1 year in the child, and blood pressure in the older adult woman.

### **1.3. Study Objectives**

The HAPIN trial will address the following specific aims: (1) using an intention-to-treat analysis, determine the effect of a randomized LPG stove and fuel intervention on health in four diverse LMIC populations using a common protocol; (2) determine the exposure-response relationships for HAP and four primary health outcomes (birthweight, stunting and severe pneumonia in infants, and blood pressure in older adults); and (3) determine relationships between the LPG intervention and both targeted and exploratory biomarkers of exposure and health. This SAP addresses a subset of the second aim, examining an exposure-response relationship between HAP exposure and severe infant pneumonia.

## **2. STUDY METHODS**

### **2.1. Trial design**

HAPIN was a randomized, two-arm intervention trial with parallel assignment. Study sites in the four countries (Guatemala, India, Peru, Rwanda) were selected and evaluated based on activities conducted in the formative research. HAPIN used a rolling recruitment process whereby each International Research Center (IRC) enrolled 800 pregnant women (one per household) and additionally up to 120 older adult women from the same households who meet inclusion/exclusion criteria (Section 4.1). Key characteristics of each study site are given in Table 2 of the HAPIN design publication. Recruitment and enrollment occurred over approximately 15 months at ~53 pregnant women/8-12 older adult women per month per IRC. All participants were followed longitudinally for ~18 months (until the child was age 1 year).

### **2.2. Randomization**

To ensure balance between arms, households have been randomly allocated to intervention or control arms after consent was given and baseline data are collected. To maintain balance of treatment assignments within each study site at the IRCs, a total of 10 randomization strata are implemented as follows.

- The India IRC stratified randomization across two sites.
- The Peru IRC stratified randomization across six sites.
- Guatemala and Rwanda have one site each.

Separate randomization lists have been generated for each field team conducting randomization at each IRC. Two randomization lists are produced for each of those field teams: one for households that include an older adult woman (OAW), and one for households that do not. Additional details on randomization of households can be found in the HAPIN protocol.

### **2.3. Sample Size Considerations**

The study population size was decided based on sample size calculation for a test of the relative risk of pneumonia associated with the randomized LPG intervention. This separate ITT analysis has been reported. We assumed a 1-year cumulative incidence rate among the control group as  $p_1 = 0.06$  [a weighted average from Mackenzie et al. 2014, Gupta et al. 2010, Mortimer et al. 2017, Broor et al. 2007, Farooqui et al. 2015]. Multiple events per child is expected for some children over the follow-up period. We assume a 10% attribution over the 1-year follow-up period, resulting in an effective sample size of  $n = 1440$  per treatment arm for pneumonia. There is no sample size calculation for the exposure-response analysis, but the power should be

like the ITT. Power of E-R models is expected to be slightly greater than the ITT if the exposure measures are complete and valid enough.

## **2.4. Trial Framework**

HAPIN is a superiority trial. While the primary intention-to-treat analysis (described in a separate document) is a test of statistical significance to evaluate whether there is a difference in the incidence of severe infant pneumonia between the intervention and control arms, the **exposure-response analysis** is a test of the association between personal exposures to household air pollutants and severe infant pneumonia.

## **2.5. Statistical Interim Analyses and Stopping Guidance**

No interim analysis will be conducted.

## **2.6. Timing of Analysis**

All analysis will be conducted once data collection and cleaning are complete, and the SAP has been approved and registered. Exposure-response analysis between severe infant pneumonia and exposure will be conducted as a standalone analysis.

## **2.7. Timing of Outcome and Covariate Assessments**

Participating households were followed from enrollment until the index child reaches (or would have reached, assuming a live birth and continued vitality) their first birthday. For the purposes of this analysis plan, severe pneumonia follow-up is through the first year of life.

HAP exposure was assessed prenatally and postnatally. The measurement periods were 24 hours. Prenatal exposures include one measurement at baseline (<20 weeks, denoted as the BL measurement in our trial) and two post-randomization (at 24-28 weeks' gestation denoted as P1; and at 32-36 weeks' gestation denoted as P2). We measured child postnatal exposures indirectly as a reconstructed average of maternal personal exposures and two area concentrations three times at ages 3 (denoted as the B1 measurement), 6 (denoted as B2) and at 12 months (denoted as B4). A validation subset of 10% of participants had double the numbers of measures, with extra measures at time points spaced between those of the main study.

Time-invariant covariates that are potential confounders and effect modifiers were collected at baseline and birth. If effects of time-varying exposures are considered, covariates that could be time-varying confounders were collected at quarterly household visits during infancy (e.g. vaccination, breast feeding).

# **3. STATISTICAL PRINCIPLES**

## **3.1. Confidence Intervals**

Confidence intervals will be presented at 95% confidence for the primary exposure-response analyses and for any subgroup analyses. For the purposes of comparability of findings with those from the intention-to-treat analyses, we will also present 98.75% confidence intervals, i.e., a familywise adjustment to account for four primary outcomes, in the Online Supplement.

## **3.2. Analysis Populations**

The **exposure-response** analyses will include all follow-up time after birth and before death in study children whose households continue participating in HAPIN and who are at risk of a new severe pneumonia episode. No person-time is contributed to the cases of death of the mother prior to birth, miscarriage, stillbirth, and withdrawal from study prior to birth. Otherwise, person-time at risk was counted from the date of birth until the earliest date among the following: age 1 year, death of child, withdrawal from the study, or migration from the study area.

Missingness may affect exposure-response relationships. If the proportion missing exposure or confounder data is <10%, our study population for primary exposure-response analyses will be restricted to those

participants with complete data. If the proportion of exposure or confounder data missing is  $\geq 10\%$ , we will consider using multiple imputation methods to reduce missing data bias and loss of power.

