**Table 1. HAP exposures measured in the trial**

Measurement time	Notation	Personal exposure in pregnant woman	Personal exposure in mother	Area concentration in kitchen	Area concentration in bedroom	Indirect measurement in children
9 – 19 weeks' gestation	BL	PM 2.5 , BC, CO				
24 – 28 weeks' gestation	P1	PM 2.5 , BC, CO				

32 – 36 weeks' gestation	P2	PM 2.5 , BC, CO				
Child is 3 months of age	B1		PM 2.5 , BC, CO	PM 2.5 , BC, CO	PM 2.5 , BC, CO	PM 2.5 , CO
Child is 6 months of age	B2		PM 2.5 , BC, CO	PM 2.5 , BC, CO	PM 2.5 , BC, CO	PM 2.5 , CO
Child is 12 months of age	B4		PM 2.5 , BC, CO	PM 2.5 , BC, CO	PM 2.5 , BC, CO	PM 2.5 , CO

The main outcome for this analysis is the same as in the intention-to-treat analysis (infant severe pneumonia). We will also analyze a set of predefined alternative definitions of pneumonia that cover a range of sensitivity, specificity, and disease severity. There were 175 HAPIN severe pneumonia during the follow-up period, among 2984 infants (6%), and there were 267 severe WHO pneumonias (9%). These respiratory endpoints are summarized in Table 2:

Table 2. Pneumonia and other respiratory outcomes	
Parameter	Definition
(HAPIN) severe infant pneumonia	
 
Presence of cough and/or difficult breathing and at least one general danger sign and primary endpoint pneumonia on a lung ultrasound or chest x-ray
 
Presence of cough and/or difficult breathing and hypoxemia (measured via pulse oximetry, SpO2)
 
Children who died but their death is attributed to pneumonia by verbal autopsy
 
 
General danger signs for all participants include any of the 5 signs of:
 
 
Unable to drink or breastfeed
 
Vomiting everything
 
Convulsions
 
Lethargy or unconscious
 
Stridor at rest
 
Severe acute malnutrition (weight-for-length z-score < -3 or weight-for-age < -3 if length is missing)
 
 
There are 4 additional general danger signs for participants <2 months of age (neonatal danger signs):
 
 
Unable to feed
 
Grunting
 
Not moving at all or moves with stimulation only
 
Severe chest indrawing
 

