As for post-natal values of  $X_{ij}$ , we will consider two approaches for measuring averages. The first will use means of values for  $\mathbf{X}$  for the  $j^{th}$  quarter using all values of personal exposures to  $PM_{2.5}$  that fall in the first quarter defined in Table 4, or the average of any prior exposures thereafter. We will consider unweighted means of the  $PM_{2.5}$  (or CO) exposures, and weighted mean of the values for  $\mathbf{X}$  considering the distances in time between the ages when personal exposures to  $PM_{2.5}$  were measured and the age at the start of the  $j^{th}$  quarter. The third approach uses a regression model to estimate infant's mean personal exposures. As children's data are missing for about 50% of post-natal measurements, we will use the mother's personal exposure measured at the same timepoint when the infant's measurement is missing. The unadjusted correlation of maternal and infant measurements is about 0.89. Prior work has shown that when using a regression model to predict time-specific infant exposures using mother's post-natal exposure and adjusted for season, weekend, and IRC, has correlation of 0.95 when compared with the infant's observed personal exposure. Using the assumption that maternal and child personal exposures measurements are similar, we anticipate that we will only have ~10% missing child exposure data. We will select the best approach for modeling exposure from the approach that leads to the least amount error in estimation of exposure (based on a root mean squared error in validation study).

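### Infants who die or leave before the 3-month visit have no specified first-quarter post-natal exposure, and neither branch of the missing-data rule commits to keeping them, although some may be primary-endpoint cases

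*SAP*

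**What the plan says.** **Time at risk.** In SAP Section 3.2, "person-time at risk was counted from the date of birth until the earliest date among the following": age 1 year, death, withdrawal or migration. A live-born child who dies or leaves at 1 or 2 months is therefore at risk until then.

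**Endpoint.** Table 2 in Section 5.1 includes in HAPIN severe pneumonia: "Children who died but their death is attributed to pneumonia by verbal autopsy". Section 5.4 repeats this.

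**Exposure.** Section 2.7 and Table 1 place the first post-natal measurement, B1, at 3 months of age. Section 6.1 uses values "that fall in the first quarter defined in Table 4, or the average of any prior exposures thereafter", and Table 4 lists B1 alone for ages up to 3 months. For gaps, Section 6.1 says "we will use the mother's personal exposure measured at the same timepoint when the infant's measurement is missing". It expects about 10% of child exposure data still to be missing after that step.

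**Missing data.** Section 3.2 states: "If the proportion missing exposure or confounder data is <10%, our study population for primary exposure-response analyses will be restricted to those" (that is, to children with nothing missing). At 10% or more, "we will consider using multiple imputation methods to reduce missing data bias and loss of power".

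**The concern.** Membership of the analysis set in the first quarter depends on reaching a visit at the end of that quarter. A pneumonia death before B1 is a primary-endpoint event and, at the same time, the reason the exposure value is missing. The missingness therefore depends on the outcome.

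A trigger based on the overall percentage missing cannot detect this, because a small number of missing infants can hold a larger share of the cases. At stake are some of the 175 events and, if early loss also varies with exposure, the exposure-response slope itself. The plan to include all follow-up after birth would also not be met in the quarter when the additional danger signs for children under 2 months apply.

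**Working it through.** **1. The plan's own figures.** 2984 infants × 4 quarters = 11,936, which agrees with the stated figure of about 12,000 infant-quarters. 175/2984 = 5.9%, stated as 6%.

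**2. Does any written rule supply a first-quarter value without B1?**
- Table 4 lists only B1 for ages up to 3 months.
- Maternal substitution uses the same timepoint, so it is again B1.
- The average of prior exposures serves later quarters only.
- Averaging the available BL, P1 and P2 values fills the prenatal term, not the post-natal term.
- The regression approach is named without its predictors. The earlier work cited for it used the mother's post-natal exposure.

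None of these gives a specified value.

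**3. What the missing-data rule does.** Ten percent is 0.10 × 2984 = about 298 infants, or 0.10 × 11,936 = about 1,194 infant-quarters. The trigger counts all missing exposure or confounder data, and about 10% missing child exposure is already expected, so which branch applies is open. Below 10%, infants without B1 leave any model that contains the post-natal term. At 10% or above, imputation is only considered.

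**4. Lost events (assumed counts; the SAP gives none).** The standard error is taken to vary as 1/√events.

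| Cases lost | Share of 175 | SE ratio |
|---|---|---|
| 5 | 2.9% | √(175/170) = 1.015 |
| 10 | 5.7% | √(175/165) = 1.030 |
| 20 | 11.4% | √(175/155) = 1.063 |

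**5. Concentration of cases (assumed).** If 60 infants (60/2984 = 2.0%) lack B1 and 10 of them are cases, risk among those dropped is 10/60 = 16.7%, against 165/2924 = 5.6% among those kept.

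**6. Bias in the risk ratio (illustration only).** Assume a true RR of 1.5, equal-sized exposure groups and 40% of cases in the first quarter. The small change in denominators is ignored.
- Loss of 20% of high-exposure and 10% of low-exposure first-quarter cases: first-quarter RR = 1.5 × 0.80/0.90 = 1.33. Overall, 1.5 × (0.6 + 0.4 × 0.80)/(0.6 + 0.4 × 0.90) = 1.5 × 0.92/0.96 = 1.44.
- Loss of 30% and 15%: first-quarter RR = 1.5 × 0.70/0.85 = 1.24. Overall, 1.5 × 0.88/0.94 = 1.40.
- Equal proportions lost: the factors cancel and RR stays at 1.5.

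The direction is not fixed. With a true RR of 1.25 across a median split, 60 infants dropped and 20 cases lost, the complete-data RR is 1.29 if losses are equal in number in the two halves, 1.15 if 75% fall in the high-exposure half and 1.03 if all do.

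**The case against.** The best defence is that the SAP does not commit to dropping anyone. With about 10% missing exposure anticipated before any confounder gaps, the imputation branch is at least as likely. Section 5.1 also leaves room for other ways of estimating infant exposure. That stands: exclusion is conditional. But considering imputation is not a plan to impute, and no text names a method for this case.

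Section 2.7 follows households to the date the child would have turned one, so a maternal B1 after an infant death is conceivable. Table 1, however, ties B1 to the child's age, Section 4.3 lists child death as an exit category, and children who left are not helped. The extra measurements in the 10% validation subset do not appear in Table 4.

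A reader might infer four stronger things that the document does not support.
- *That the complete-data branch will certainly apply.* Comparing early losses alone (for example 60/11,936 = 0.5%) with the trigger is wrong, because the trigger counts all missingness.
- *That verbal-autopsy deaths are shut out of the endpoint.* Only deaths before B1 are affected.
- *That the prenatal estimate must lose these infants.* Section 6.1 speaks of modelling the two periods separately but then writes a sum of both terms, and Section 5.2 allows adjustment sets for either. A prenatal-only model would keep them.
- *That vaccination and breastfeeding are unknown for them.* Section 2.7 says only that "covariates that could be time-varying confounders were collected at quarterly household visits during infancy". It does not say what was known about a child who died earlier.

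**Conclusion.** The gap is real. Infants who die or leave before B1 are at risk and can be cases, yet the plan assigns them no post-natal exposure and does not commit to keeping them under either branch. The missingness depends on the outcome whenever the early loss is a pneumonia death.

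The size cannot be read from the SAP. The figures of 2.9% to 11.4% of events and about 1.5% to 6% in standard error rest on an assumed 5 to 20 lost cases. Bias toward the null is possible but not shown. It needs case loss that differs by exposure, and equal proportional loss costs only events. In the first illustration, loss twice as high among exposed first-quarter cases moves an RR of 1.50 to 1.44 or 1.40. The point should be settled before the analysis because it concerns primary-endpoint cases in the primary model.

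**What to change.** In Sections 3.2 and 6.1 (with Table 4):
- State that every live-born infant at risk in the first quarter stays in the primary analysis, whatever the overall percentage missing.
- Where B1 is absent because of death or exit, multiply impute first-quarter exposure, and any missing 3-month covariates, from the maternal prenatal values (P2, P1, BL), season, IRC and the outcome.
- Report the complete-data analysis as a sensitivity analysis, with the number of first-quarter cases and of verbal-autopsy deaths lacking B1.

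Multiple imputation is preferable to a single value predicted from P2 or P1. A single prediction would make exposure error differ by case status, and the post-natal term would largely repeat the prenatal term in the same model.

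The cost is some wording and one imputation step on data already collected. The drawback is that late-pregnancy maternal exposure predicts early-infancy exposure imperfectly. In time it is not much further away: for an event 4 weeks after a birth at 40 weeks (assumed), P2 at 32 to 36 weeks lies 8 to 12 weeks before, and B1 at about 13 weeks lies about 9 weeks after.

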## 4. STUDY POPULATION

### 4.1. Eligibility

Pregnant women were eligible to participate in the study if they fulfilled the following inclusion and exclusion criteria at screening:

*Inclusion criteria:*

- Offspring of a confirmed pregnancy (hCG positive blood or urine test)
- Offspring of a pregnant woman aged 18 to less than 35 years (via self-report)
- Offspring of a pregnant woman 9 to less than 20 weeks' gestation confirmed by ultrasound
- Offspring of a singleton pregnancy (one fetus confirmed by ultrasound)
- Viable fetus with normal fetal heart rate (120-180 beats per minute) at time of ultrasound
- Lives in study area
- Uses biomass stove for cooking predominantly
- Agrees to participate with informed consent
- Continued pregnancy at the time of randomization confirmed by self-report

*Exclusion criteria:*

- Currently smokes cigarettes or other tobacco products
- Plans to move permanently outside study area in the next 12 months
- Uses LPG stove predominantly, or is likely to use LPG predominantly, in the near future

If two eligible pregnant women lived in the same household and were interested in participating, the one with the earliest gestational age was chosen to participate.

The severe pneumonia exposure-response analysis includes all live-born children in households that continued participating in the HAPIN trial through trial exit.

